Answer Yes or No

QUESTION	YES	NO
Are you 18 years or older?		
Do you suffer from crampy-like pain located in the lower abdomen associated to menses?		
Have you ever been diagnosed with any of the following: endometriosis, adenomyosis, myomatous uterus?		
Have you ever been diagnosed with hearing impairment or require the use of hearing devices?		
Have you ever been diagnosed with Cancer, Diabetes, Cardiac disease, neurologic disease, or endocrine disease?		
Do you currently use or have used in the last two months oral contraceptives or other hormonal contraceptive method?		
Have you ever been diagnosed with any psychiatric condition or have you ever required psychiatric drug use?		
Have you ever received additional music education besides that provided in your school?		
Have you ever been pregnant?		

SUPPLEMENT 2. QUESTIONNAIRE: Demographic and personal data

Personal data

- Age:
- Studying program:
- Ongoing semester:
- Marital status :
- Have you ever received additional music education besides that provided in your school? (Select one) SI NO
 - If your answer was YES, please specify:

Medical History

Have you been diagnosed with any disease? YES NO

Specify: _____

Have you required surgery? YES NO

Specify: _____

Is there any important disease in close family member (father, brother, grandparents, uncles/aunts)? YES NO

Specify: _____

Have you suffered an accident? YES NO

Specify: _____

Gynecologic history

Please complete the following:

- Pregnancy: ___ Losses (Abortions): ___ Born children: ___
- Age at menarche:
- How many days do you have your menses? ___
- How many days do your menses last? ___

Regarding the pain associated to your menses:

1. Which of the following describes better your pain? (Select one)
 - a. Opressive (squeeze-like)
 - b. Crampy (spasm)
 - c. Burning (ardor)
 - d. Other: _____
2. At what time do you start feeling pain? (Select one)
 - a. 48-24 before my menses

- b. < 24 hours before my menses
- c. The same day of my menses
- d. First 24 hours after my menses
- e. Other: _____

3. How much time do you feel pain during your menses? (Select one)

- a. < 10 hours
- b. 10-24 hours
- c. 24-48 hours (1-2 days)
- d. 48-72 hours (2-3 days)
- e. Other: _____

4. Which was the first time you felt pain with your menses? (Select one)

- a. With my first menarche
- b. 1-6 months after my menarche
- c. 6-12 months after my menarche
- d. 1-2 years after my menarche
- e. Other: _____

5. Did you take any drug for pain relief during your last menses? YES NO

Drug name: _____

Used doses (Number of tablets): _____

E.g. Ibuprophen 4 tablets of 800 mg

6. Did you use any form of non-pharmacological strategy for pain relief during your last menses? YES NO

Specify: _____

For this part please read carefully instructions

Visual analog scale (VAS) consist of a 10 cm line. The line is marked with a 0 in one side and 10 in the other, and consider 0 as the least possible intensity and 10 as the greatest. For using the tool you have to put a mark that represents the perceived intensity that better answers the question.

7. Consider 0 (I have never felt pain during menses) and 10 (I always feel my worst kind of pain). Which is your usual pain associated to menses?

SUPPLEMENT 4. Questionnaire for the day of the intervention

STUDIED VARIABLES

The following document will be of exclusive use for the researchers during the day that the study is conducted. TIME: _____

Please answer the following questions.

1. With a single mark please answer. How much pain are you feeling right now? Consider 0 as "I'm not feeling any pain" y 10 "I'm feeling the worst pain of my life" (patient must answer by herself).

0  10

2. Please answer the following questions with: Never, Sometimes, Most of the time o Always.

Question	Never	Sometimes	Most of the time	Always
Have you felt nervous or anxious lately				
Have you felt fearful lately				
Have you been irritated or have you panicked easily				
Have you felt down				
Have you felt tremulous				
Have you felt headache, pain on your back, or pain on your neck				
Have you felt weak and fatigue easily				
Have you felt palpitations or elevated heart rate				
Have you felt dizzy lately				
Have you felt nausea or stomach disturbances lately				

3. Answer Yes or No. Would you take an analgesic drug or other would you do another analgesic strategy at this moment? If Yes, please specify:

4. At this moment how much time have you felt pain?

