2.2. Specific objectives

- To describe demographic, medical history, gynecologic and obstetric history of the studied population.
- To describe the analgesic strategies and drugs used for pain relief in primary dysmenorrhea in the studied population.
- To evaluate the quantified perception of usual pain in primary dysmenorrhea using a VAS in college students 18 years or older.
- To explore if a difference exist in the acute quantified perception of pain in primary dysmenorrhea, using a VAS, among 18-year or older college students prior to receive the music or silence interventions.
- To evaluate if a difference exist in the acute quantified perception of pain in primary dysmenorrhea, using a VAS, among 18-year or older college students after receiving the music or silence interventions.
- To explore if a difference exist in the change of quantified pain perception using a VAS in primary dysmenorrhea, from the moment prior to the intervention until the moment after the intervention, among 18-year or older college students that listened to music or stayed in silence.
- To evaluate if a difference exist in the acute quantified perception of pain in primary dysmenorrhea, using a VAS, among 18-year or older college students 3 to 6 hours after receiving the music or silence interventions
- To explore if a difference exist in the change of quantified anxiety in primary dysmenorrhea, evaluated with the Zung's scale, from the moment prior to the intervention until the moment after the intervention, among 18-year or older college student that listened to music or stayed in silence.
- To evaluate if a difference exist in requirements of pharmacological analgesics for pain relief in primary dysmenorrhea, among college students that received music compared to those that stayed in silence after the intervention, and 3 to 6 hours after the intervention.
- To evaluate if differences exist in heart rate, systolic blood pressure, and diastolic blood pressure, using a calibrated digital sphygmomanometer, between 18-year or older college students receiving music and those staying in silence.

3. Material and Methods

Design

A prospective and single blinded randomized clinical trial will be conducted. Two groups will be compared, the experimental group will receive a music intervention, and control group will stay under the same condition and the same time with headphones in silence.

Study population

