- **Strategies used for pain relief:** simple questions will be used to ask drugs and doses used for pain relief, and non-pharmacological treatment use.
- **Pain intensity:** a VAS will be used to measure pain intensity during menses. The following question will be used “How intense is your pain at this moment?” where 0 is “I do not feel any kind of pain” and 10 is “I am feeling the worst pain of my life”.
- **Anxiety:** a 10 item short version of the self-applied scale for the measurement of anxiety by Zung will be used (49). Zung’s scale was developed in 1971 (50), it is of free use, and has been studied and validated in Spanish and in Colombian population (49, 51). De la Ossa et al., evaluated internal consistency and functional structure of the original scale compared to a 5 item and 10 items short versions, finding high consistency for all three especially for the 10-item version (49). The short version

consist of items 1, 2, 3, 4, 6, 7, 8, 11 and 15 (Supplement 5). Each item has 4 possible answers (never, some times, most of the time, all the time), and the patient should only give one per item.

- **Acute analgesic requirements:** the following questions will be used: 1. *In this moment would you like to take any kind of drug for pain relief? If the answer is yes, the generic name of the drug will be asked.*
- **Analgesic requirements during the day:** a collecting item that requests the following: 1. Drug name; 2. Drug presentation; 3. Dose used; 4. Time for using the drug.
- **Vital signs:** using a calibrated sphygmomanometer the following will be measured: systolic blood pressure, diastolic blood pressure, mean blood pressure, and heart rate. Blood pressure will be measured at level of the radial artery of the dominant arm. Measurement will be done with the patient sitting and with the arm extended at the level of the heart window.

Procedure

An open enrollment will be offered to all female students of at least 18 years old from the School of Medicine and Health Sciences from the university. The researchers will approach students that want to participate at any moment, and eligibility criteria will be assessed using a simple questionnaire based on inclusion and exclusion criteria.

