The study will be explained in detail to the students that are found to be eligible. A speech will be design prior to enrollment to avoid disclosing different information among participants. The speech will mention that: "...they will participate in a research about the effects of music in primary dysmenorrhea, in which they will be compared to a control group..."¹. The speech will explain the rest of the details for the experimental part of the study. Finally, they will be requested to sign informed consent for participation.

After signing informed consent, patients will be allocated by computer generated randomization. Randomized codes will be generated and information about the study will be put in envelops. The information inside the envelope will not disclose the allocated group.

The intervention will be conducted after pain associated to menses begins. The information in the envelopes will contain instructions for the intervention. These will explain how to access the intervention, additionally, it will contain information on what to do while enrolled to the study. The patient will be instructed to avoid taking drugs or doing any analgesic therapy before receiving the allocated intervention. Nevertheless, it will be clarified to the patient that she can do any form of analgesia if needed but it should be informed to researchers. The intervention will be avoided if patients have to endure pain for 12 hours or more, or those that use any form of analgesia before the intervention. Both of these will be clearly instructed to participants. Patients that can't receive the interventions due to the afore-mentioned situations will not be excluded as they can receive the intervention at any other menstrual cycle.

Patients will contact the researchers for the intervention, at that moment, patient will give the coded number and researchers will identify a package to give (package A or package

¹ *[not in the original protocol] - Note: the final speech did not disclose the experimental group or the main outcome (pain) as requested by IRB for approval (communication DVN021-1-088 and approval communication DVN21-1-099-CEI856) - .*

B)¹. The researcher that gives the package will not be involved in data collection nor will have knowledge of them. The other researcher will not know which package was given to the student. After receiving the package, the other researcher will guide the patient to the place where the intervention will be conducted.

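### The VAS items behind the primary endpoint ask about current pain without naming menstrual pain, so other pain could enter the score; a cheap rewording would remove the ambiguity

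*Combined protocol and SAP*

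**What the plan says.** The specific objectives (section 2.2) include a between-group comparison of "the change of quantified pain perception using a VAS in primary dysmenorrhea". Under Sample calculation, H0 and H1 are written for the change in acute pain in primary dysmenorrhea from VAS2 (before the session) to VAS3 (after it), and that change is named the main endpoint.

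Under Variables and measurement tools, the Pain intensity entry says that "a VAS will be used to measure pain intensity during menses". The question given there is "How intense is your pain at this moment", and the lower anchor is "I do not feel any kind of pain".

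The forms use different words. Supplement 4 asks "How much pain are you feeling right now" before and after the session, and Supplement 5 repeats it for VAS4 at 3 to 6 hours. The zero on these forms is again the absence of any pain. Neither the question nor the anchor mentions menses or a body site.

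The usual-pain scale, VAS1 (Supplement 2, item 7), does: "Which is your usual pain associated to menses".

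**The concern.** The hypothesis is about one pain, while the item, read literally, is about all current pain. A woman whose cramps have gone but who has a headache cannot truthfully mark zero, and her mark may follow the headache. VAS1 carries the qualifier and the three acute scales do not, although two of those three form the endpoint.

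Two consequences are possible. If other pain drives the mark and neither arm changes it, the expected difference between music and silence gets smaller. If music eases the other pain, that relief would be reported as relief of dysmenorrhea; this is a problem of interpretation that no sample size cures. Neither could be sorted out afterwards, because no form records whether another pain was present when the VAS was marked.

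**Working it through.** **1. Item against construct**

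| Scale | Where | Names menstrual pain? | Used in VAS2 − VAS3? |
|---|---|---|---|
| VAS1 | Supplement 2, item 7 | Yes | No |
| VAS2 | Supplement 4, before the session | No | Yes |
| VAS3 | Supplement 4, after the session | No | Yes |
| VAS4 | Supplement 5, 3 to 6 hours | No | No |
| Protocol text for the acute VAS | Variables and measurement tools | Stated purpose yes; question and zero anchor no | – |

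**2. The plan's sample size**

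Inputs from Sample calculation: one-sided α = 0.01 (z = 2.33), power 0.90 (z = 1.28), SD σ = 2, difference Δ = 1.5, allocation 1:1.

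n = 2 × (2.33 + 1.28)² × 2² / 1.5² = 2 × 13.0321 × 4 / 2.25 = 46.34, rounded up to 47 per group. The plan's figure is reproduced.

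**3. When other pain has no effect on the contrast**

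Let M be menstrual pain and O other pain, and suppose the mark is M + O. If O is the same at both times, (M₂ + O) − (M₃ + O) = M₂ − M₃. Stable additive pain cancels, and neither the difference nor the power changes.

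**4. When it dilutes the contrast**

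Suppose a share f of women in each arm mark a different pain altogether, and neither arm changes that pain. The expected difference becomes 1.5 × (1 − f). The documents give no value for f, so the values below are assumptions. SD is held at 2.

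Power comes from a two-sample t-test with 47 per arm (92 degrees of freedom), one-sided α = 0.01. The standard error is 2 × √(2/47) = 0.4126, and the noncentrality is the difference divided by 0.4126.

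| f (assumed) | Difference | Noncentrality | Power |
|---|---|---|---|
| 0 | 1.50 | 3.64 | 0.895 |
| 5% | 1.425 | 3.45 | 0.859 |
| 10% | 1.35 | 3.27 | 0.815 |
| 20% | 1.20 | 2.91 | 0.705 |

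The normal approximation, which is the basis of the plan's formula, gives 0.905, 0.870, 0.828 and 0.720 for the same rows.

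**5. When relief is misattributed**

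If O falls more under music than under silence, the difference in VAS2 − VAS3 includes that fall. The documents offer nothing from which to size it.

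**The case against.** The strongest reply is that the setting supplies the missing words. Under Procedure, "The intervention will be conducted after pain associated to menses begins", and Supplement 6 tells the woman to make contact when that pain starts. The history questionnaire and VAS1 are completed before VAS2, so she has just answered a block of questions on menstrual pain. VAS3 repeats the question in the same place after 30 minutes. Supplement 4 also asks how long she has felt pain without naming which pain, and that makes sense only for menstrual pain, so the forms appear to use the bare word as shorthand. The general objective speaks of the painful experience in primary dysmenorrhea, which a global rating could be said to serve. The supplements are English renderings with Spanish residue, so the wording women saw may differ.

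Most of this stands, and it is why the point is small. It does not remove the mismatch: H0 and H1 are narrower than the general objective, and the zero anchor explicitly covers pain of every kind. The added note under Procedure also says that the final speech did not disclose pain as the main outcome, so the briefing may not have directed women to the target pain. The context is weakest for VAS4, which is answered hours later, but VAS4 is outside the primary contrast.

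A reader might go further in three ways that the documents do not support:

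- **That other pain does enter and bias the result.** The documents show only that it could. Randomization balances other pain between arms in expectation, so its presence alone creates no false difference.
- **That the plan expected other pain at the session, because a form asks "Have you felt headache, pain on your back, or pain on your neck".** That item belongs to the short Zung anxiety scale and is not tied to the VAS. Lumbar pain, moreover, counts as dysmenorrhea under inclusion criterion 3a.
- **That power is lost in every case.** Stable additive pain cancels.

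**Conclusion.** The point holds as a modest weakness in how specifically the primary outcome is measured. The wording of the acute scales and their zero anchor do not match the pain named in the hypotheses, and nothing on the forms would allow a correction later. Whether any woman's mark was affected cannot be told from the documents.

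The size rests wholly on an assumed share of marks that follow unresponsive other pain. It runs from no loss (power about 0.90) to about 0.86, 0.82 and 0.71 at 5%, 10% and 20%, with 47 per arm, SD 2 and one-sided 0.01. These figures describe the adverse case, in which the mark follows the other pain entirely and that pain does not move. Given the session context, the low end is the more plausible. Misattribution remains possible but cannot be sized.

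**What to change.** Use one identical question for VAS2, VAS3 and VAS4, in the Pain intensity entry under Variables and measurement tools and in Supplements 4 and 5, and name the target pain as VAS1 does. For example: *How intense is the pain associated with your menses at this moment?*, with 0 = *I do not feel any menstrual pain*. This also removes the present difference in wording between the protocol text and the forms. Check the Spanish forms for the same point.

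The cost is one reworded item and anchor on two forms and in the protocol. The planned 47 per group does not change. The small downside is that a woman with several pains must judge the menstrual one separately.

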5. HR____ BP____ MBP____

Please complete the following after the intervention.

1. With a single mark please answer. How much pain are you feeling right now?
Consider 0 as "I'm not feeling any pain" y 10 "I'm feeling the worst pain of my life" (patient must answer by herself)

0 _____ 10

2. Please answer the following questions with: Never, Sometimes, Most of the time o Always.

Question	Never	Sometimes	Most of the time	Always
Have you felt nervous or anxious lately				
Have you felt fearful lately				
Have you been irritated or have you panicked easily				
Have you felt down				
Have you felt tremulous				
Have you felt headache, pain on your back, or pain on your neck				
Have you felt weak and fatigue easily				
Have you felt palpitations or elevated heart rate				
Have you felt dizzy lately				
Have you felt nausea or stomach disturbances lately				

3. Answer Yes or No. Would you take an analgesic drug or other would you do another analgesic strategy at this moment? If Yes, please specify::

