Female students 18 years or older matriculated to one of the programs registered at the School of Medicine and Health Sciences from Universidad del Rosario. Students volunteering to participate, those giving written consent to participate in this protocol, and those complying our eligibility criteria:

- Inclusion criteria
 1. Students at least 18 years old.

2. With legal and cognitive capacity to give written consent to participate.
3. Patients that comply to characteristics and definition of primary dysmenorrhea according to literature (2, 4-8):
 - a. Crampy-like pain located in the inferior abdomen, lumbar region, or inguinal region
 - b. Pain initiating no longer than 24 hours prior to the first bleeding during the menstrual cycle
 - c. Pain lasting 24-72 hours
 - d. Pain that always occurs with menses
4. Ability to understand and respond all questionnaires and measuring tools.

- Exclusion criteria
 1. Prior diagnosis of endometriosis, adenomiosis, myomatous uterus, or any other gynecologic cause of secondary dysmenorrhea.
 2. Any degree of hearing impairment or use of auxiliary hearing devices.
 3. Diagnosed cognitive deficit or neurologic condition.
 4. Prior diagnosis of psychiatric disease, use of anxiolytic or anti-depressive drugs, or history of substance or alcohol abuse in the last two years.
 5. Diagnosis of cancer, diabetes mellitus, or cardiac disease.
 6. Advanced music training (receiving advanced music theory in addition to normal music education given by schools).
 7. Irregular menstrual cycles.
 8. Diagnosis of any endocrine disease.
 9. Current use, or use in the last two months, of oral contraceptive or other hormonal contraceptive method.
 10. Prior gestation or labor.

Variables and measurement tools:

- **Demographic data:** age, current studying semester, religion, and civil status will be collected.
- **Medical history:** medical, surgical and obstetric history will be collected.
- **Menstrual cycle data:** the following will be collected: 1. Menarche; 2. Time between each cycle; 3. Menses duration; 4. Contraceptives use.
- **Pain associated to menses:** using a visual analogue scale (VAS), the usual pain associated to menses will be collected. The VAS uses a 10 cm line that goes from 0 “I have never felt pain during my menses” to 10 “I always feel the worst of pain of my life during menses”.

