The SPSS for Mac, version 20, software was used for data analyses. For qualitative variables, frequency and percentages measurements will be used. For quantitative variables, central tendency measurements, variability and variance coefficients was used.

The primary endpoint for the study will be the effect of music in pain in dysmenorrhea. The secondary endpoints will be the impact in analgesic requirements, vital signs, and anxiety quantification. Comparative analysis will be performed to evaluate if a relationship between the level of pain and analgesic requirements, anxiety levels, and vital signs exist. Finally, multivariate analysis (MANCOVA) will be conducted to further test statistical significance for the pain relieving effect of music ($p < 0.01$).

4. Ethical considerations

This study is classified as minimum risk in accordance to the established regulations by the Resolution 008430 of 1993 from the Ministry of Health of Colombia (Scientific, technical, and administrative norms for the research in health).

All participants from the study will enroll and participate on their own desire and no person will be obligated to enroll, continue or complete the study participation. The study will not expose participants to drug interventions, surgical procedures or diagnostic procedures, physical therapy or other type of intervention that will add potential risks to physical integrity of participants. The study will be conducted in the Quinta de Mutis of the Universidad del Rosario, Bogota city. Therefore, no exposure to ambient risks will be related to this research. The sole intervention patients will receive is music through headphones. For conducting this research all recommendations from Helsinki declaration by the World Medical Associations will be considered.

5. Activity chronogram

ACTIVITY	MES															
	1	2	3	4	5	6	7	8	9	10	11	12	13	14	15	16
PROTOCOL DEVELOPMENT																
SEARCH FOR ADDITIONAL FUNDING IF REQUIRED AND IRB SUBMISSION																
DATA COLLECTION																
DATA ANALYSES																
PATIENT RECRUITMENT ACCORDING TO ELIGIBILITY CRITERIA																

¹ [not in the original protocol] – Note: before doing the first intervention it was deemed more appropriate to perform an interim analysis than a pilot study -.

INTERVENTION AND DATA COLLECTION FROM INCLUDED PATIENTS			
DATA ANALYSES			
DISCUSSION OF DATA ANALYSES			
COMPLETE RESULTS REPORT			
MANUSCRIPT PREPARATION			
SUBMISSION FOR PUBLICATION			

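### One item of the Zung anxiety form asks about back pain, so part of an anxiety difference, and of the planned pain–anxiety association, could be pain relief

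*Combined protocol and SAP*

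**What the plan says.** The Data analyses part of section 3 ranks anxiety as secondary: "The secondary endpoints will be the impact in analgesic requirements, vital signs, and anxiety quantification". The matching objective in section 2.2 is "To explore if a difference exist in the change of quantified anxiety in primary dysmenorrhea, evaluated with the Zung's scale", comparing the arms on change from before to just after the intervention.

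Under Variables and measurement tools, "a 10 item short version of the self-applied scale for the measurement of anxiety by Zung will be used". "Each item has 4 possible answers (never, some times, most of the time, all the time"), but the plan gives the answers no numerical values and no rule for combining them.

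The same ten items are printed in Supplement 4 before and after the intervention, and in Supplement 5 for 3–6 hours later. Two matter here: "Have you felt headache, pain on your back, or pain on your neck" and "Have you felt nausea or stomach disturbances lately".

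Inclusion criterion 3a describes the qualifying pain as "Crampy-like pain located in the inferior abdomen, lumbar region, or inguinal region".

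The Data analyses part also plans a comparative analysis to "evaluate if a relationship between the level of pain and analgesic requirements, anxiety levels, and vital signs exist". It names a MANCOVA for the pain effect at p < 0.01 without listing covariates. It has no item-level analysis, no score without the bodily symptoms, and no adjustment of anxiety change for pain change.

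**The concern.** The intervention is given once menstrual pain has begun and within its first 12 hours, so a student whose cramps reach the lumbar region may answer the pain item on the strength of the pain that qualified her. Randomisation balances this at baseline. It does not balance the change, because the alternative hypothesis is that pain falls more with music. If that is true, the pain item can fall more in the music arm while anxiety stays the same. The overlap therefore works in the scenario where the trial succeeds on pain and an anxiety benefit is most likely to be reported beside it.

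The planned pain–anxiety analysis does not separate the two, since the anxiety score entering it contains a pain item. At stake is how a secondary result is interpreted.

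**Working it through.** **The plan's own figure.** The only sample-size figure is for the primary endpoint. With the inputs in Sample calculation (z values 2.33 and 1.28, σ = 2, Δ = 1.5, 1:1 allocation):

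n = 2 × (2.33 + 1.28)² × 2² / 1.5² = 2 × 13.0321 × 4 / 2.25 = 46.34, rounded up to 47 per group.

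This reproduces. The documents give no effect size, SD or significance level for anxiety.

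**Share of the score.** Assume items are scored 1–4 and summed.
- Range of the total: 10 × (4 − 1) = 30 points (10 to 40).
- Headache/back/neck-pain item: 3 / 30 = 10%.
- With the nausea/stomach item: 6 / 30 = 20%.

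(The text lists nine item numbers for the short version, while the printed form has ten. I use the printed form.)

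**What the pain item contributes.** Write the total as T = A + B, with B the pain item and A the other nine. The between-arm difference in mean change is D(T) = D(A) + D(B). With no effect on the other nine items, D(A) = 0 and D(T) = D(B). Further, D(B) = p × d, where p is the share of students whose pain reaches the back and d is the extra fall on that item, in categories, with music among them. The documents give neither. As assumptions: p = 0.5 and d = 0.5 give 0.25 points; p = 0.5 and d = 1 give 0.5; p = 1 and d = 1 give 1.0, an extreme in which every student has back pain and falls a full category more with music.

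**Chance that this alone is significant in favour of music.** With 47 per group and an assumed SD of change in the total of 2 to 5 points:

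chance = Φ( D(B) / (SD × √(2/47)) − z ), with √(2/47) = 0.2063 and z = 1.960 (two-sided 0.05) or 2.326 (one-sided 0.01).

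Example: D(B) = 0.5, SD = 2 gives 0.5 / 0.4126 = 1.212; 1.212 − 1.960 = −0.748; Φ = 22.7%.

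| D(B), points | Two-sided 0.05: SD 2 | SD 5 | One-sided 0.01: SD 2 | SD 5 |
|---|---|---|---|---|
| 0 | 2.5% | 2.5% | 1.0% | 1.0% |
| 0.25 | 8.8% | 4.3% | 4.3% | 1.9% |
| 0.5 | 22.7% | 7.0% | 13.3% | 3.3% |
| 1.0 | 67.9% | 16.1% | 53.9% | 8.7% |

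The table shows how the result depends on the assumptions. It does not estimate the bias.

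**The association.** Cov(pain, T) = Cov(pain, A) + Cov(pain, B). To the extent that B tracks menstrual pain, the second term is positive even if the other nine items are unrelated to pain. That part of the association comes from the shared content.

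**The case against.** The strongest reply is that the overlap is narrow and slow to act, and most of that stands.

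- A reader might infer from criterion 3a that every participant has lumbar pain. The three sites are alternatives, and the screening form in Supplement 1 asks only about the lower abdomen. Nothing says how many students have back pain. The item also covers headache and neck pain.
- A reader might treat the stomach item as a second pain item and quote 20%. Nausea or stomach upset is not lower-abdominal cramp and is not in criterion 3a. The direct overlap is one item, 10% of the range under the assumed scoring.
- A reader might call the anxiety score a second measurement of the primary outcome. The primary VAS asks about intensity at that moment; the Zung items ask how often something has been felt. Half an hour of relief need not change a frequency answer. Four of the ten items, including the stomach item, carry the word lately. The pain item does not, so this damping is less certain for it.
- The protocol reports high internal consistency for the 10-item version, and validation of Zung's scale in Spanish and in a Colombian population. That supports keeping the total. It does not address use during menstrual pain, when a back-pain answer may have another source.

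What remains is that one scored item overlaps with a qualifying pain site, the trial expects that pain to change differently by arm, and the plan does not separate the two.

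**Conclusion.** The point holds as a limited problem of interpretation. Part of a music-versus-silence difference in the anxiety total could be pain relief, and the planned pain–anxiety relationship is partly inflated by the shared item. The share of range is 10%, or 20% if the stomach item is counted, both resting on the assumed 1–4 summed scoring. The size of the bias is unknown and may be small.

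It would be tempting to conclude that an anxiety difference cannot be read as less anxiety at all. The documents do not support that: nine items are not pain items, eight if the stomach item is also set aside, and a shift across them would count as evidence. Nor do they support assuming a full-category extra fall on both items (2.0 points), which would take the chance at two-sided 0.05 to 99.8% (SD 2) or 49.2% (SD 5); the documents give no basis for a shift of that size.

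Anxiety is secondary and its objective is worded as exploratory. The primary endpoint and the 47 per group are unaffected.

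**What to change.** Add a short paragraph to Data analyses:

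1. State the scoring rule and keep the 10-item total as the main anxiety score.
2. Pre-specify a sensitivity analysis of the arm comparison without the headache/back/neck-pain item (nine items; range 9–36 under 1–4 scoring), and another also without the nausea/stomach item (eight items; range 8–32).
3. Compute the pain–anxiety association without the pain item.
4. Describe an anxiety effect as distinct from pain relief only if the reduced-item results are consistent with the total.

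The answers are already collected item by item at every time point, so forms and procedures do not change. The cost is that the reduced scores are not validated short forms and will be slightly less reliable, which is why they support the total and do not replace it.
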